### **5.2.2 Assessment of asthma exacerbations**

During the study, an asthma exacerbation will be defined as a worsening of asthma symptoms that leads to any of the following:

- A temporary bolus/burst of systemic corticosteroids (at a dose above one level higher than the current titration step) for at least 3 consecutive days to treat symptoms of asthma worsening; a single depo-injectable dose of corticosteroids will be considered equivalent to a 3-day bolus/burst of systemic corticosteroids. Note: Per-protocol up-titration of the OCS dose to one level higher is not necessarily considered to be an exacerbation event
  - Patients who experience an exacerbation during the screening period (between Visits 1 and 2) can be granted an extension of the screening period to ensure that a patient recovers from an asthma exacerbation and the OCS dose is stabilized.
- An emergency room or urgent care visit (defined as evaluation and treatment for  $<24$  hours in an emergency department or urgent care center) due to asthma that required systemic corticosteroids (as per the above)
- Inpatient hospitalization (defined as admission to an inpatient facility and/or evaluation and treatment in a healthcare facility for  $\geq 24$  hours) due to asthma

The Investigator must justify the decision for defining an event of worsening asthma as an exacerbation and record it in the source documents and eCRF. An asthma exacerbation that occurs within 7 days of the last dose of systemic steroids, prescribed for a prior exacerbation, will be counted as the same exacerbation event.

The patient may remain in the study after an exacerbation and continue to receive study drug if the Investigator judges that it is medically appropriate for the patient to do so and will be managed as per the details provided in Section [5.2.3](#).

Reasonable attempts should be made by the Investigator to bring the patient into the study site for patient-initiated asthma worsening, particularly when it results in additional treatment being prescribed. Study site evaluations for asthma worsening may occur as an unscheduled visit or as part of a routine center visit if the worsening happens to occur in line with a scheduled visit. A copy of the medical record should be obtained for exacerbations evaluated and treated at non-study sites (eg, by the primary care provider or at an emergency department/hospital). Details should be entered into the exacerbation eCRF in a timely fashion. Changes in concomitant medications due to exacerbations must be recorded in the appropriate module of the eCRF.

### **5.2.3 Management of asthma exacerbations during treatment period**

Patients who experience an exacerbation during the treatment period may remain on the study drug at the Investigator's discretion. Asthma exacerbations will be treated with oral or other systemic corticosteroids according to standard clinical practice.

- **Induction phase:** If a patient experiences an exacerbation during the induction phase, the start of the OCS dose reductions may be delayed. After the OCS bolus/burst to treat an exacerbation is complete, the patient may be returned to a one-step higher dose level (or more if considered necessary by the Investigator) than what was prescribed when the exacerbation occurred. The Investigator may decide to maintain the same OCS dose. The patient's OCS dose should be stable for at least two weeks before entering the OCS reduction phase
- **Reduction phase:** If a patient experiences an exacerbation during the reduction phase, the Investigator may do one of the following for at least two weeks after completion of the OCS bolus/burst:
  - The patient may be returned to a one-step higher dose level (or more if considered necessary by the Investigator) than what was prescribed when the exacerbation occurredor
  - The same OCS dose may be maintained at a stable dosage and then OCS down-titration may be continued once the patient recovers from the exacerbation

Further dose reductions during this phase will be considered as per the Investigator's opinion. After recovery from the first exacerbation, the patient will be allowed to proceed with another attempt to reduce their OCS dose; however, they would follow a lower speed of OCS down-titration (reductions every 4 weeks) ([Table 3](#)).

In case of a second exacerbation, no further OCS dose reduction will be allowed, and the patient will continue the same dose or will return to a one-step higher dose level (or more as considered necessary by the Investigator) than what was prescribed when the exacerbation occurred. The patient will then enter the maintenance phase and continue the same dose through the end of study.

- **Maintenance phase:** If a patient experiences an exacerbation during the maintenance phase, the length of the maintenance phase will not be extended; and the patient will continue on 3 doses of benralizumab Q8W. After the OCS bolus/burst is complete, the patient may then be returned to a one-step higher dose level (or more if considered necessary by the Investigator) than the OCS dose they were on when the exacerbation occurred, or the Investigator may decide to maintain the same OCS dose throughout the maintenance phase.

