## 2.2 Secondary objectives

Secondary Objective	Outcome Measure
To assess the sustained reduction of daily OCS dose while not losing asthma control during approximately 6 months after the end of OCS down-titration (maintenance phase) in adult patients with severe eosinophilic asthma treated with benralizumab 30 mg SC	
Key outcome measure
 
 
Change in daily OCS dose from the end of OCS reduction phase to the end of the maintenance phase (EOT visit)
 
Time to first increase in OCS dose during maintenance phase, after achieving the minimum OCS dose during the OCS reduction phase
 

To assess the effect of OCS down-titration protocol on asthma control in adult patients with severe eosinophilic asthma treated with benralizumab 30 mg SC	
Key outcome measure
 
 
Asthma Control Questionnaire 6 (ACQ-6) scores at baseline (Visit 2), Visit 3, end of OCS reduction phase, and monthly from end of OCS reduction phase to end of maintenance phase (EOT visit)
 
Change from baseline in ACQ-6 to Visit 3, end of OCS reduction phase, and end of maintenance phase (EOT visit)
 
Responder analysis of ACQ-6 scores from Visit 2 through end of maintenance phase
 

To assess the effect of OCS down-titration protocol on quality of life in adult patients with severe eosinophilic asthma treated with benralizumab 30 mg SC	
Key outcome measure
 
 
Change from baseline (Visit 2) in St. George's Respiratory Questionnaire (SGRQ) total scores to the end of maintenance phase (EOT visit)
 
Responder analysis of SGRQ total scores at the end of maintenance phase
 

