Dose reduction of OCS should be interrupted if the patient suffers an asthma exacerbation (Section 5.2.3) or in case the Investigator considers the patient to be having a significant deterioration of his/her asthma disease (Section 5.1.2.1). After the OCS bolus/burst to treat an exacerbation is completed, or after recovery from an asthma deterioration, the Investigator may either return the OCS dose to a one-step higher dose level (or more if considered necessary by the Investigator) than what was prescribed when the exacerbation or asthma worsening occurred or continue with the same OCS dose, which must be maintained at a stable dosage for at least two weeks.

After recovery from the first exacerbation or asthma deterioration, the patient will be allowed to proceed with another attempt to reduce their OCS dose; however, the patient will follow a lower speed for OCS down-titration (reductions Q4W; [Table 3](#)).

In case of a second exacerbation or asthma deterioration, no further OCS dose reduction will be allowed, and the patient will remain on the same OCS dose or return to a one-step higher dose level (or more as considered necessary by the Investigator) than what was prescribed

when the exacerbation/worsening occurred. The OCS dose reduction phase will then be terminated, and the patient will enter the maintenance phase. Further details are provided in Section [5.2.3](#).

Patients who experience asthma exacerbations that require evaluation in an urgent care center or emergency department, hospitalization, or temporary increase of systemic steroids (bolus/burst dosing) will be managed as per details in Section [5.2.3](#).

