#### **4.2.3 Maintenance phase**

A patient will enter the approximately 24- to 32-week maintenance phase when they reach an OCS dose of 0 mg/day (or lowest OCS dose possible in case no further OCS down-titration is allowed because of the presence of AI as measured by cortisol levels or in case of inadequate asthma control) without losing asthma control. This could be earlier if OCS dose reduction fails due to clinical deterioration or if the patient experiences an asthma exacerbation. The duration of the maintenance phase will depend on when the patient enters the maintenance phase relative to the dosing cycle of benralizumab. During this phase, patients will continue benralizumab Q8W for 3 doses and then the EOT visit will be scheduled 8 weeks ( $\pm$  7 days) after the last dose of benralizumab (assessments performed as per [Table 1](#)). However, if during this period, the patient experiences asthma deterioration or an exacerbation, the length of the maintenance phase will not be extended and the patient will continue on 3 doses of benralizumab Q8W. Additionally increases in the maintenance OCS dose due to an asthma exacerbation is permitted per investigator discretion. Patients who experience an asthma exacerbation that requires evaluation in an urgent care center or emergency department, hospitalization, or temporary increase of systemic steroids (bolus/burst dosing) will be managed as per details in Section [5.2.3](#).

Patients who have Complete AI or Partial AI at the end of the OCS Reduction phase, will undergo a final morning cortisol test (and if required, ACTH stimulation test for indeterminate result) approximately 1-2 weeks prior to end of the OCS Maintenance phase (prior to EOT visit).

Patients will return the ePRO at the EOT visit. Completion of the treatment will be registered in IWRs/IVRs at the EOT visit for each patient. After stopping study drug, the patient will be adjusted to a post-study asthma maintenance regimen (which may include a respiratory biologic, if needed), per Investigator discretion.

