### **5.1 Efficacy assessments**

#### **5.1.1 Assessment of OCS dose**

All patients who meet eligibility criteria and enter the study will receive open-label benralizumab and reduce their OCS dose until the patient reaches an OCS dose of 0 mg/day (or lowest OCS dose possible in case no further OCS down-titration is allowed because of the presence of AI as measured by cortisol levels or in case of inadequate asthma control) as per the details provided in Section [4.2.2](#) and the schedule provided in [Table 2](#) and Section [5.1.2](#)

No further reductions will be made to OCS dose after completion of the reduction phase, and the patient will enter an approximately 24- to 32-week maintenance phase. In case of exacerbations, patients will be managed as per details provided in Section [5.2.3](#). Additionally, in case the patient experiences asthma deterioration or an exacerbation, increase in the maintenance OCS dose is permitted per investigator discretion.

All OCS dose changes will be documented in the source documentation and recorded in the appropriate eCRF form. Moreover, in case of OCS reduction being temporarily interrupted (in case of an exacerbation or asthma deterioration) or permanently interrupted (exacerbation, asthma deterioration, AI based on cortisol tests, or occurrence of an adrenal crisis), the reason should be documented in the appropriate eCRF, and reduction will be done slowly as per [Table 3](#).

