3.2.2 Time to first increase in OCS dose

There are two types of increase in OCS dose: asthma-related increase and maintenance OCS dose increase. Asthma-related OCS dose increase includes any increase associated with asthma (asthma maintenance or treatment of asthma exacerbations or asthma-related AEs or signs/symptoms of AI). An increase to treat non-asthma-related AEs will be excluded. For maintenance OCS dose increase, only those which result in an increase in maintenance dose will be counted as an event. If patients have an OCS burst to treat an exacerbation but then return to the original maintenance dose, this will not count as an event. If patients have an exacerbation resulting in an increase in maintenance dose, the time of the event is the end of the exacerbation ; otherwise the time of the event is the first day of the maintenance dose

increase. Cases where patients have an ICS burst or a systemic corticosteroid burst (via intravenous / intramuscular route) to treat an asthma exacerbation will also be counted as an event of asthma-related OCS dose increase, and the start date of the exacerbation will be the time of the event.

Time to first asthma-related increase in OCS dose and time to first maintenance OCS dose increase during the maintenance phase from achieving the final OCS dose during the reduction phase will be secondary outcome variables, and are calculated as follows:

Start date of first increase in OCS dose during the maintenance phase – Date 1st achieved the final OCS dose in the reduction phase + 1.

The date that the final OCS dose of the OCS reduction phase is 1st achieved is defined as the date of the last initiation of that dose during the OCS reduction phase. The final OCS dose of the OCS reduction phase is defined in section 3.1.

If a patient withdraws from the study before reaching the first increase in OCS dose or does not increase their OCS dose by the end of the maintenance phase, the patient will be censored at the withdrawal date or at the end date of the maintenance phase, whichever is earlier.

The proportion of patients whose OCS dose is not increased due to asthma exacerbation or worsening within 6 months will be a supportive outcome variable for this endpoint. The proportion of patients whose maintenance OCS dose is not increased within 6 months will be another supportive outcome variable.

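### Protocol 5.2.3 holds the OCS dose fixed in maintenance after a second reduction-phase exacerbation while three other passages allow increases; read literally, it rules out the maintenance-dose-increase event and sets dose change to zero for those patients

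*Protocol*

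**What the plan says.** The reduction-phase bullet of Protocol 5.2.3 covers a second exacerbation. It bars further reduction and leaves the patient either on the current dose or one or more steps higher. It then adds: "The patient will then enter the maintenance phase and continue the same dose through the end of study".

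Three passages describe OCS dosing in maintenance differently:

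- Protocol 4.2.3: "Additionally increases in the maintenance OCS dose due to an asthma exacerbation is permitted per investigator discretion".
- Protocol 5.1.1: "in case the patient experiences asthma deterioration or an exacerbation, increase in the maintenance OCS dose is permitted per investigator discretion".
- Protocol 5.2.3, maintenance-phase bullet, on an exacerbation in that phase: "After the OCS bolus/burst is complete, the patient may then be returned to a one-step higher dose level". A larger step, or no change, is also left to the investigator.

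None of the three excludes patients whose taper ended at a second exacerbation. Protocol 4.2.2 describes the same second event and stops at entry to maintenance: "The OCS dose reduction phase will then be terminated, and the patient will enter the maintenance phase". The Synopsis, Protocol 1.4.3 and SAP 1.2 also lack the clause about keeping the dose.

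One of the two key measures for the sustained-reduction objective in Protocol 2.2 is "Time to first increase in OCS dose during maintenance phase, after achieving the minimum OCS dose during the OCS reduction phase". The other is the change in daily OCS dose from the end of reduction to the end of maintenance. SAP 3.2.2 splits the time-to-event measure into an asthma-related increase and a maintenance dose increase. For the latter: "For maintenance OCS dose increase, only those which result in an increase in maintenance dose will be counted as an event".

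**The concern.** The same patients fall under two instructions, and nothing ranks one above the other. A site could reasonably treat the sentence written for these patients as overriding the general permission. Another could just as reasonably apply the general permission to everyone in maintenance.

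The choice matters for the sustained-reduction objective. A dose that stays level because the protocol holds it there looks the same in the data as one that stays level because asthma control was kept on benralizumab. If some sites hold the dose and others raise it, similar patients contribute differently to both key measures, depending on which paragraph was followed.

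**Working it through.** No planned figure bears on this point. The only precision figure in the design is the 4.1-point distance from a 50% success rate at 600 patients (Protocol 8.2). The exact Clopper-Pearson calculation reproduces it at 4.08, but it describes the primary proportion and is not used below. The check is a comparison of passages, followed through the SAP definitions.

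**1. The passages side by side**

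| Place | Who it covers | OCS dose in maintenance |
|---|---|---|
| Protocol 5.2.3, reduction bullet, last sentence | Second exacerbation in reduction | Kept unchanged; no exception |
| Protocol 4.2.3 | Anyone in maintenance | May rise after an exacerbation |
| Protocol 5.1.1 | Anyone in maintenance | May rise after deterioration or exacerbation |
| Protocol 5.2.3, maintenance bullet | Anyone exacerbating in maintenance | May rise one step or more, or stay |
| Synopsis, Protocol 1.4.3 and 4.2.2, SAP 1.2 | Second exacerbation or deterioration | Dose at entry only; silent on later changes |

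The restriction therefore rests on one sentence, and that sentence is triggered by a second exacerbation only.

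**2. Is the sentence needed only to prevent a renewed taper?** No. The sentence before it already bars further reduction, and Protocol 5.1.1 bars reductions for everyone once the reduction phase is complete.

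**3. Change in dose (SAP 3.2.1).** Change = final maintenance dose at EOT or IPD − final dose of the reduction phase. Let d be the dose carried into maintenance. Under the literal sentence both terms equal d, so change = d − d = 0. This assumes no protocol deviation. It also assumes that the SAP's final reduction-phase dose is d. SAP 3.1 falls back on an earlier stable dose when the recorded one is not held for 4 weeks without worsening, so the difference need not be zero in such a case.

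**4. Maintenance-dose increase (SAP 3.2.2).** An event needs a maintenance dose above d; a burst followed by return to d does not count. With d fixed, no event can occur. The patient is censored at withdrawal or at the end of maintenance, whichever is earlier.

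**5. Asthma-related increase (SAP 3.2.2).** This includes increases given to treat an exacerbation, and systemic steroid bursts by injection or infusion also count. Protocol 5.2.3 opens by allowing such treatment throughout the treatment period. The event can occur under either rule.

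**6. Under the permissive passages** both event types can occur and the change in dose can be positive.

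**The case against.** The strongest reply is that Protocol 5.2.3 is organised by phase. On that view the reduction bullet only sets the dose carried into maintenance, and the maintenance bullet then governs any later exacerbation for everyone. Keeping the dose would be the default when nothing new happens, not a ban on increases. The silence of the other accounts of the second event fits this. The reading is plausible, but no text states it, and step 2 shows that the sentence is not needed to stop further tapering. The ambiguity stands.

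The reply is right on several further points. A reader might infer that these patients cannot have the secondary-endpoint event at all. SAP 3.2.2 does not support that, because the asthma-related event remains open. A reader might also infer that the protocol leaves treatment of a further exacerbation undefined. It does not: burst treatment is stated, and only the maintenance dose after the burst is in doubt. The words about the end of the study might seem to clash with the post-study regimen in Protocol 4.2.3. Even so, both measures end by EOT, IPD or the end of maintenance, so that point cannot affect them.

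The SAP also separates part of the problem already. SAP 4.2.6.2 repeats the time-to-increase analysis for patients reaching 0 mg and by degree of reduction achieved, and tabulates events by reason. That helps, but patients are grouped by the reduction they reached, not by why the taper stopped. A patient stopped by two exacerbations can still fall in one of the partial-reduction groups.

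**Conclusion.** The concern holds as a conflict of wording with a defined consequence for two secondary measures. Under the literal sentence in Protocol 5.2.3, these patients cannot have the maintenance-dose-increase event, and their change in maintenance dose is zero by rule, subject to the assumptions in step 3.

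No effect size is claimed. The size would depend on the share of patients entering maintenance after a second exacerbation, how many of them would otherwise have had an increase, and how many sites applied the sentence literally. The documents give none of these. A reader might be tempted to assume values and set the product against the 4.1-point distance. That would compare assumed inputs with the precision of a different endpoint, and it would treat every site as holding the dose. Nor do the documents say that these patients are the ones most likely to need more OCS.

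The study is descriptive and tests no hypothesis, so what is at stake is how the sustained-reduction results are read.

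**What to change.** **Protocol.** Reconcile the last sentence of the reduction-phase bullet in 5.2.3 with 4.2.3, 5.1.1 and the maintenance-phase bullet of 5.2.3, so that one statement governs OCS increases in maintenance for patients who entered after a second exacerbation. Which rule should stand is for the sponsor to decide.

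**SAP.** In 4.2.6.1 show change in OCS dose, and in 4.2.6.2 time to first maintenance increase, separately for patients who stopped down-titration because of two or more exacerbations. SAP 4.2.5.1 already forms this group for baseline characteristics. The separate row cannot tell a dose held by rule from one held by control, but it keeps the two from being merged and read together as sustained reduction.

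The cost is one clarifying sentence in the protocol and one extra row in two outputs. No new data are needed.

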### 5.2.4 Laboratory safety assessments

Laboratory safety assessments (listed in [Table 4](#)) will be performed in a central laboratory. For information on methods of collection, assessment, labelling, storage, and shipment of samples, please refer to the separate laboratory manual. Safety samples will be collected according to the schedule provided in [Table 1](#).

Laboratory results should be reviewed by the Investigator/authorized delegate and evaluated for abnormalities. Any laboratory abnormalities considered to be significant in the Investigator/authorized delegate's judgement should be reported as AEs, as described in [Section 6](#).

The copy of the laboratory results report should be signed and dated by the Investigator/authorized delegate and retained at the study site.

